7.2. Participant Discontinuation/Withdrawal From the Study

Study withdrawal is defined as the permanent cessation of further participation in any study assessment before its planned completion.

The primary reason for permanent study withdrawal will be recorded.

If possible, an EDV and safety follow-up visit(s) should be conducted when the participant is withdrawn from the study. Study sites should make every effort to schedule the EDV and safety follow-up visit(s) as follows:

- Participants on efgartigimod PH20 SC treatment should attend the EDV 7 days after the participant's final IMP administration; the safety follow-up visits should occur 4 and 8 weeks after the participant's final IMP administration.
- Participants in the observation period should attend the EDV within 7 days after the last contact with the site and a safety follow-up visit 8 weeks after the previous contact.

The following circumstances will result in permanent discontinuation and withdrawal from the study:

- Participant withdrawal of consent
- Sponsor request
- Investigator request due to noncompliance with study protocol procedures

If the participant withdraws consent to participate in the study, the sponsor can retain and continue to use any data collected before consent was withdrawn. Future research on samples collected from participants who withdraw consent to participate in the study will not be affected unless the participant also withdraws the consent for future research.

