8.2.1. Efficacy Measures

8.2.1.1. Assessment of BP Disease Status and OCS Dose Monitoring

The BP disease status will be assessed by the investigator at on-site visits according to the definitions/criteria presented in the [Definitions of Terms](#). During these visits, the investigator will examine the participant for new lesions (transient or nontransient), record the daily concurrent BP therapy (if applicable) administered to the participant since the last visit, including the dose, adjust the daily OCS dose (taper, stop, reinstate, or increase; if applicable) based on the participant's BP disease status, and record treatment failure.

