2.2 PHASES, PERIODS AND TIME POINTS

2.2.1 *Analysis phases, periods and subperiods*

All assessments and events will be allocated to analysis phases, periods and subperiods as defined in below table.

Table 2: Analysis phase, period and subperiod definition

Phase	Period/Subperiod	Start	End
For participants who don't receive the first IMP administration at the ARGX-113-2010 baseline visit^a, the first phase will be the observation phase.			
For participants who receive the first IMP administration at the ARGX-113-2010 baseline visit^a, the first phase will be the treatment phase.			
Observation		Date of baseline visit in ARGX-113-2010, with 00:00 added as time part	
For participants with a subsequent treatment period:
 
First IMP administration date/time – 1 minute.
 
For other participants:
 
Date of week 48 or EDV visit^c, with 23:59 added as time part.
 
For participants who don't have a week 48 or EDV visit: date of last contact, with 23:59 added as time part.

	Statistical Analysis Plan	
ARGX-113-2010	Final analysis	Final 1.0 of 29APR2025

Phase	Period/Subperiod	Start	End
Treatment	Treatment period 1/ On IMP treatment	
For participants with first IMP administration at the baseline visit:
 
Date of baseline visit in ARGX-113-2010, with 00:00 added as time part.
 
For participants with a previous observation phase and who initiate treatment:
 
First IMP administration date/time
	
For participants with a subsequent Off IMP subperiod:
 
Last IMP administration date/time in treatment period 1.
 
For other participants:
 
Date of week 48 or EDV visit^c, with 23:59 added as time part.
 
For participants who don't have a week 48 or EDV visit: date of last contact, with 23:59 added as time part.

	Treatment period 1/ Off IMP treatment	Last IMP administration date/time in treatment period 1 + 1 minute	
For participants with a subsequent treatment period:
 
First IMP administration date/time in next treatment period – 1 minute.
 
For other participants:
 
Date of week 48 or EDV visit^c, with 23:59 added as time part.
 
For participants who don't have a week 48 or EDV visit: date of last contact, with 23:59 added as time part.

Treatment period 2 is applicable for participants who re-initiate IMP administration after a previous Off IMP subperiod^b.			

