Treatment	Treatment period 2/ On IMP treatment	First IMP administration date/time in treatment period 2	
For participants with a subsequent Off IMP subperiod:
 
Last IMP administration date/time in treatment period 2.
 
For other participants:
 
Date of week 48 or EDV visit^c, with 23:59 added as time part.
 
For participants who don't have a week 48 or EDV visit: date of last contact, with 23:59 added as time part.

	Treatment period 2/ Off IMP treatment	Last IMP administration date/time in treatment period 2 + 1 minute	
Date of week 48 or EDV visit^c, with 23:59 added as time part.
 
For participants who don't have a week 48 or EDV visit: date of last contact, with 23:59 added as time part.

	Statistical Analysis Plan	
ARGX-113-2010	Final analysis	Final 1.0 of 29APR2025

Phase	Period/Subperiod	Start	End
Follow-up		End of previous phase + 1 minute	Date of last contact, with 23:59 added as time part.

- ^a First IMP administration is considered to occur on the ARGX-113-2010 baseline visit if the date of first IMP administration equals the scheduled baseline visit start date (SVSTDTC) or end date (SVENDTC), or if the first IMP administration occurs on an unscheduled baseline visit. In either case, the first phase starts with SVSTDTC of the first scheduled or unscheduled baseline visit.
- ^b A new treatment period is considered for participants with relapse after achieving CR or PR while being off concurrent BP therapy for ≥ 8 weeks before protocol amendment 2 was effective, or at the investigator's discretion after protocol amendment 2 was effective. For programming purposes, a new treatment period will be considered if a participant has a gap of at least 4 weeks (28 days) between two consecutive IMP administrations that cannot be attributed to missed visits or non-efficacy related reasons documented on the study drug administration eCRF form.
- ^c SVENDTC of the last scheduled or unscheduled week 48 or early discontinuation visit will be used.

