4. EFFICACY, PHARMACODYNAMIC, AND IMMUNOGENICITY ANALYSES

4.1 EFFICACY AND QUALITY OF LIFE

All efficacy endpoints are secondary endpoints in this OLE study and will be evaluated descriptively.

4.1.1 *Available data*

Investigators report the participant's best disease status in episodes with start and end date (no CDA, CDA, CR, PR, Relapse and Treatment failure). Furthermore, BPDAI activity and total score, IGA-BP scores and itch NRS are collected over time.

Quality of life is assessed over time using the ABQOL, DLQI and EQ-5D-5L questionnaires.

The health impact of long-term glucocorticoid use is assessed via the Aggregate Improvement Score (AIS) and Cumulative Worsening Score from the Glucocorticoid Toxicity Index (GTI) and via the GTI Specific List (GTI-SL).

4.1.2 *Derivation rules*

The following endpoints will be derived **for each treatment period separately**:

- 1) Participants achieving CR while off OCS for ≥ 8 weeks (CROff). A participant will be considered a CROff responder if the following criteria are met simultaneously for ≥ 8 weeks (56 days):
 - The participant's reported disease status is CR
 - The participant is off OCS therapy
 - The participant does not receive any rescue therapy (as indicated by the investigator on the eCRF)

Else, the participant will be considered a CROff non-responder. Participants who already have the disease status CR at day 1 of the treatment period or who are off OCS therapy at day 1 of the treatment period or who receive rescue therapy at day 1 of the treatment period, will be considered non-evaluable for this endpoint and will be excluded from this analysis for the corresponding treatment period.

Note: the rules for assessing the OCS dose on a given day are described in section 3.4.2. Similarly, these rules can be used to assess whether rescue therapy is received on a given day. Additionally for rescue therapy, a frequency of PRN (pro re nata, or 'as needed') will be interpreted as a dose of 1 time per week.

- 2) Participants achieving CR or PR while off OCS for ≥ 8 weeks (CR/PROff). A participant will be considered a CR/PROff responder if the following criteria are met simultaneously for ≥ 8 weeks (56 days):
 - The participant's reported disease status is CR or PR (continuously or alternately)
 - The participant is off OCS therapy
 - The participant does not receive any rescue therapy (as indicated by the investigator on the eCRF)

	Statistical Analysis Plan	

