Else, the participant will be considered a non-responder for CROff without IMP. Participants who enter the ARGX-113-2010 study under protocol version 3 (26 April 2024) or 4 (02 May 2024) will be considered non-evaluable for this endpoint. Furthermore, participants who were randomized to the placebo arm in the ARGX-113-2009 study and who enter the ARGX-113-2010 study in the observation phase, will be considered non-evaluable for this endpoint in the observation phase.

- 6) Participants achieving CR or PR while off both OCS and efgartigimod PH20 SC for ≥ 8 weeks (CR/PROff without IMP). A participant will be considered a

	Statistical Analysis Plan	
ARGX-113-2010	Final analysis	Final 1.0 of 29APR2025

responder for CR/PROff without IMP if the following criteria are met simultaneously for ≥ 8 weeks (56 days):

- The participant's reported disease status is CR or PR (continuously or alternately)
- The participant is off OCS therapy
- The participant is off IMP
- The participant does not receive any rescue therapy (as indicated by the investigator on the eCRF)

Else, the participant will be considered a non-responder for CR/PROff without IMP. A participant will be considered non-evaluable for this endpoint using the same rules as for CROff without IMP.

- 7) Duration of sustained remission will be calculated for participants achieving CR while off both OCS and efgartigimod PH20 SC for ≥ 8 weeks (i.e., responders for CROff without IMP) within a treatment period.
 - Start date of sustained remission is 1 week (7 days) after the last IMP administration in the treatment period
 - End date of sustained remission is:
 - the start date of first relapse after achieving CROff without IMP
 - the start date of a (next) treatment period
 - the start date of OCS therapy after achieving CROff without IMP
 - the start date of a rescue therapy after achieving CROff without IMP
 whichever comes first. If none of the above occurs, the participant will be censored at the end date of the study (end date of last phase).
 - Duration of sustained remission (in days) = end date - start date + 1
- 8) Relapse will be evaluated for participants having or achieving CDA, CR or PR during the treatment period (or observation phase). The evaluation period for relapse is till the end of the treatment period (or observation phase) in case a (next) treatment period starts, or else till the end of the study. Only the first relapse in a treatment period (or observation phase) will be considered.

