- 9) Time to relapse:
 - Start date is the first day with status CDA, CR or PR in the treatment period (or observation phase)
 - End date is:
 - the start date of first relapse after having or achieving CDA, CR or PR
 - the end date of the study (end date of last phase), if no relapse
 - Time to relapse (in days) = end date - start date + 1
- 10) For participants with relapse, severity of (first) relapse will be calculated as the BPDAl total score at the onset of relapse (use the first available nonmissing BPDAl total score in the interval of relapse) minus the BPDAl total score at the preceding visit (use the most recent preceding visit for which a nonmissing BPDAl total score is available). Severity of relapse will be categorized as <0 , $0- <10$, $10- <20$, $20- <30$, or >30 .

	Statistical Analysis Plan	
ARGX-113-2010	Final analysis	Final 1.0 of 29APR2025

The following endpoints will be derived **overall**:

- 11) Changes and percent changes from study baseline will be calculated for BPDAI activity and total score.
- 12) Changes from study baseline will be calculated for itch NRS 24-hour average and worst scores.
- 13) C-GTI: Composite Glucocorticoid Toxicity Index comprises the Aggregate Improvement Score (AIS) and the Cumulative Worsening Score (CWS). Details of AIS and CWS derivations are specified in appendix 9.1.
- 14) A total ABQOL score is calculated as the sum of all 17 items score 0 to 3 with higher score indicating worse condition. Missing items are imputed with the average score of the present items if at least half (9) of the items are present. The total score is rounded to the highest integer.
- 15) Changes from study baseline will be calculated for EQ-5D-5L VAS score, DLQI score and total ABQOL score.

4.1.3 *Presentation of results*

Efficacy results will be presented for the ROL analysis set, unless mentioned otherwise. For tables by analysis visit, only the study baseline and last assessment analysis visits will be shown. Other analysis visits will be included in listings.

A frequency tabulation will be created for the number and percentage of participants who achieved CROff at least once during the study (i.e., in any treatment period). The table will also present the number of participants who are evaluable for the endpoint at least once during the study. This number will serve as denominator for the percentage calculation. This table will be based on the SAF analysis set.

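### Time to relapse and duration of sustained remission are censored at an undefined date of last contact, which can fall after the last disease-status assessment

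*SAP*

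**What the plan says.** **Censoring date.** SAP section 4.1.2, item 9, ends time to relapse at the first relapse or at "the end date of the study (end date of last phase), if no relapse". Item 7 censors duration of sustained remission at the same date when relapse, a new treatment period, OCS and rescue therapy are all absent. Both endpoints are listed as Kaplan-Meier tables (14.2.1.8 and 14.2.1.6).

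**What that date is.** SAP section 2.2.1, Table 2, ends the follow-up phase at the "date of last contact, with 23:59 added as time part". The observation and treatment phases fall back on the same date: "For participants who don't have a week 48 or EDV visit: date of last contact, with 23:59 added as time part". The SAP does not define date of last contact.

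**When relapse can be observed.** Protocol section 8.2.1.1: "The BP disease status will be assessed by the investigator at on-site visits". Audio or video assessment appears only in the COVID-19 provisions (protocol Appendix 5, Table 8). SAP section 4.1.1 has investigators report "best disease status in episodes with start and end date".

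**The concern.** A relapse enters these analyses through an investigator's assessment, while event-free time runs on to the last contact of any kind. If that contact comes after the last assessment, the interval between them is counted as relapse-free, or as sustained remission, although disease status was not assessed in it. This sits badly with SAP section 2.3.1, which plans an observed-cases analysis without imputation: counting the interval as event-free in effect imputes no relapse.

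The protocol foresees such contacts. Participants who miss visits are pursued by telephone or letter (section 7.3). SAEs and AESIs are followed until resolution, stabilization or another explanation (section 8.4.3), and all infections are AESIs (section 8.4.6). The second route could also move a completer's last contact past the EoTP + 8 weeks visit.

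Durability of response is a stated secondary objective, and the rule can only err in the favourable direction. No planned sensitivity analysis covers it. The last-assessment visit in SAP section 2.2.6 applies to scores and laboratory-type data, not to disease status.

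**Working it through.** The documents give no withdrawal rate, relapse rate or expected median for these endpoints, so there is no planned figure to reproduce.

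**1. Trace of the censoring date.** Items 7 and 9 lead to the end of the last phase. With a week 48 visit or EDV, the last phase is follow-up, which ends at last contact. Without either visit, the preceding phase also ends at last contact. No route leads to the last disease assessment as such.

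**2. Direction.** The Kaplan-Meier estimate is S(t) = product over event times of (1 − d/n), where d is the number of events and n the number at risk. Moving a censoring date later leaves every d unchanged and can only raise n. So S(t) cannot fall, and the medians cannot shorten.

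**3. One participant.** SAP formula: end date − start date + 1. Assume CDA from day 1, last assessment on day 113 and no relapse.
- Censored at the last assessment: 113 − 1 + 1 = 113 days.
- Last contact 28 days later (one visit interval on drug): 141 − 1 + 1 = 141 days.
- Last contact 56 days later (one visit interval off drug): 169 − 1 + 1 = 169 days.
- Last contact is itself the assessed visit: 113 days under both rules.

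The participant gains exactly the gap.

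**4. Size across a cohort, by simulation.** All inputs except the visit intervals (protocol section 4.1) and the study lengths are assumptions:
- exponential relapse with 48-week probability 20%, 40% or 60%;
- independent withdrawal of 10%, 20% or 30%, uniform over 336 days;
- assessments every 28 or 56 days, with a gap equal to the interval, or no gap;
- every withdrawn participant is given the gap, and completers none, with follow-up to day 392 (56 weeks);
- 400,000 participants per scenario.

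Change in the 48-week Kaplan-Meier relapse estimate, last contact minus last assessment, in percentage points:

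| 48-week relapse | Withdrawal | 28-day gap | 56-day gap |
|---|---|---|---|
| 20% | 10% | −0.16 | −0.31 |
| 20% | 20% | −0.33 | −0.67 |
| 20% | 30% | −0.53 | −1.06 |
| 40% | 10% | −0.27 | −0.55 |
| 40% | 20% | −0.58 | −1.17 |
| 40% | 30% | −0.92 | −1.87 |
| 60% | 10% | −0.33 | −0.70 |
| 60% | 20% | −0.71 | −1.47 |
| 60% | 30% | −1.13 | −2.35 |

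With no gap the change is 0.00 in all nine combinations. The median is reached only at 60% relapse. There it is about 254 days when censoring at the last assessment. It lengthens by between 256.1 − 253.7 = 2.4 days (10% withdrawal, 28-day gap) and 270.8 − 254.5 = 16.3 days (30% withdrawal, 56-day gap).

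**The case against.** The strongest reply is that the gap will often be zero. Protocol section 7.2 states: "If possible, an EDV and safety follow-up visit(s) should be conducted when the participant is withdrawn from the study". The schedules of activities mark a disease assessment at the EDV, F1, F2 and EoTP + 8 weeks visits, so a participant whose last contact is one of these gains nothing. An unanswered call or letter is not a contact, and section 7.3 tells sites to reschedule the missed visit when they do reach someone. Nothing says that SAE or AESI follow-up updates the date used in Table 2. Relapse involves lesions or pruritus that participants can notice, unscheduled visits exist for suspected new lesions, and episodes carry dates, so a relapse found later can be dated between visits. The planned listings of visit dates and censoring reasons would let affected cases be found.

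Most of this stands, and it limits the size of the problem. It does not remove it. The post-withdrawal visits are conditional on being possible, Table 2 itself provides for participants with neither a week 48 visit nor an EDV, and date of last contact is left open.

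Two stronger readings are tempting, but the documents do not support them:
- A reader might infer that withdrawn participants as a group are credited with unassessed time. Only those whose last contact is later than their last assessment are, and the documents do not say how many that is.
- A reader might infer a larger bias for sustained remission because few participants contribute. Small numbers reduce precision; they do not of themselves increase bias. Off-drug visits are 8 weeks apart, which allows wider gaps. But item 7 admits only participants with at least 56 days of CR off OCS, efgartigimod and rescue therapy, and item 5 makes those who entered under protocol version 3 or 4 non-evaluable. Few early leavers without a later assessment are likely to qualify.

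**Conclusion.** The point holds for participants, withdrawn or completers, whose last contact is later than their last disease-status assessment. For them the rule adds event-free time equal to the gap; for everyone else it has no effect. The direction is certain: time to relapse and duration of sustained remission can only be lengthened.

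The size cannot be obtained from the documents. Under the assumptions above, the 48-week relapse estimate changes by 0 to about −2.4 points and the median, where reached, by up to about 16 days. The upper end needs 30% withdrawal with a 56-day gap for every withdrawn participant, so the real effect is probably small. Withdrawal related to disease activity, which the simulation does not model, could make it larger.

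Severity is minor. The endpoints are secondary and descriptive, no hypothesis is tested, the crude proportion with relapse does not use the censoring date, and no primary safety endpoint is touched.

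**What to change.** In SAP section 4.1.2, items 7 and 9, censor participants without an event at the date of their last recorded disease-status assessment (on-site, or audio/video where used) on or before the end of the last phase. Keep date of last contact for phase duration and adverse-event follow-up, and define it in section 2.2.1.

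The cost is a line in each item and one extra date derivation. Medians may become slightly shorter. If every last contact proves to be an assessed visit, the results will not change.

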ABQoL=Autoimmune Bullous Disease Quality of Life questionnaire; AE=adverse event; BP=bullous pemphigoid; BPDAl=Bullous Pemphigoid Disease Area Index; CR=complete remission; DLQI=Dermatology Life Quality Index; ECG=electrocardiogram; eCRF=electronic case report form; EDV=early discontinuation visit; EFG=efgartigimod PH20 SC; efgartigimod PH20 SC=efgartigimod for SC administration coformulated with rHuPH20; EoTP=end-of-treatment period (visit); F1/F2=follow-up visits 1 and 2; GTI=Glucocorticoid Toxicity Index; GTI-AIS=GTI Aggregate Improvement Score; GTI-CWS=GTI Cumulative Worsening Score; GTI-SL=GTI Specific List; IGA-BP=Investigator Global Assessment of Bullous Pemphigoid; NA=not applicable; NRS=numerical rating scale; OCS=oral corticosteroids; PBMC=peripheral blood mononuclear cell; PD=pharmacodynamics; PK=pharmacokinetics; PR=partial remission; QoL=quality of life; rHuPH20=recombinant human hyaluronidase PH20; SC=subcutaneous; SoA=schedule of activities; UNS=unscheduled visit; W=week

Note: Assessments indicated in gray font will only be recorded on the ARGX-113-2009 eCRF and not on the ARGX-113-2010 eCRF.

^a The baseline visit will occur on the same day as the EoTP visit of ARGX-113-2009. All baseline assessments will be performed before administration of efgartigimod PH20 SC. Assessments do not need to be repeated if performed as part of the ARGX-113-2009 EoTP visit.

^b Day X applies when efgartigimod PH20 SC is initiated (refer to Section 6.3). Efgartigimod PH20 SC treatment will be started on day X, which can be the same day as the day the relapse is confirmed. Subsequent visits will be relative to day X, except for the EoTP visit that will take place 48 weeks after baseline for all participants.

- ^c Participants who stopped receiving efgartigimod PH20 SC after rollover but before protocol amendment 2 is effective will enter the observation period with visits every 8 weeks. Efgartigimod PH20 SC will be initiated at the investigator's discretion or if relapse occurs during the study. Participants who initiate efgartigimod PH20 SC must follow the SoA in [Table 2](#) as of day X (refer to [Section 6.3](#) for more details).
- ^d Visit F1 (EoTP + 4 weeks) is only applicable for participants receiving efgartigimod PH20 SC at week 48.

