Adverse events will be allocated to phases as described in section 5.1.2. Concomitant therapies and procedures will be allocated to phases and (sub)periods as described in section 3.3.2. All other assessments will be allocated to phases and (sub)periods based on the assessment date/time. In case of (partially) missing date/time fields disabling allocation of an assessment to phases or (sub)periods, information from the visit label, time point label and the protocol schedule of activities will be used to allocate to the correct phase.

For efficacy assessments without time part, an assessment on the day of switch from observation phase to treatment phase will be considered as part of the treatment phase. Likewise, an assessment on the day of switch from treatment period 1 to treatment period 2 will be considered as part of treatment period 2.

2.2.2 *Baseline and change from baseline*

Study baseline is defined as the first available and nonmissing value at the baseline visit (scheduled or unscheduled) in ARGX-113-2010. This value corresponds with the value at the EoTP visit in ARGX-113-2009 (and is copied over into the database of ARGX-113-2010 at SDTM level).

Change from baseline is defined as:

- Change from baseline at time point t = value at time point t – baseline value.

Percentage change from baseline at time point t is defined as follows:

- When baseline value is not zero: $100 * ((\text{value at time point } t - \text{baseline value}) / \text{baseline value})$
- When both baseline value and value at time point t are zero: 0
- When baseline value is zero and value at time point t is not zero: not calculated

For immunogenicity assessments, the study baseline selection will be performed by sample (not by parameter) in order to keep the ADA and NAb results of a sample together. Furthermore, values resulting in an unevaluable ADA status are given the lowest priority when the selection is made.

For evaluation of PD parameters, a treatment period-specific baseline (TPnB) will be defined:

	Statistical Analysis Plan	
ARGX-113-2010	Final analysis	Final 1.0 of 29APR2025

- For a treatment period, TPnB is the last available and non-missing value prior to the first IMP administration in the treatment period. Assessments on day 1 of a treatment period without time collection or with time information exactly equal to the time of first IMP administration and which are planned predose will be considered as predose.

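### A date-only relapse that starts on the day efgartigimod is first given or restarted can, read literally, be counted in neither the old nor the new analysis period

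*SAP*

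**What the plan says.** **Allocation (SAP 2.2.1).** The general rule is "All other assessments will be allocated to phases and (sub)periods based on the assessment date/time". The exception is limited to efficacy records that have no time: "an assessment on the day of switch from observation phase to treatment phase will be considered as part of the treatment phase". For a restart, "an assessment on the day of switch from treatment period 1 to treatment period 2 will be considered as part of treatment period 2". In SAP Table 2 the observation phase, or the Off IMP part of treatment period 1, ends one minute before the next first dose.

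**How relapse is recorded (SAP 4.1.1).** Investigators report the "best disease status in episodes with start and end date". No time is mentioned.

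**How relapse is counted (SAP 4.1.2).** Relapse is evaluated per treatment period and for the observation phase, in participants who have or reach CDA, CR or PR in that period or phase. Under item 8, "The evaluation period for relapse is till the end of the treatment period (or observation phase) in case a (next) treatment period starts". Under item 9 the event date is "the start date of first relapse after having or achieving CDA, CR or PR"; without a relapse, time runs to the end of the study. Under SAP 4.1.3 only the first evaluation of each participant enters the time-to-relapse table.

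**When dosing follows relapse (Protocol 1.3, Table 2 footnote b).** "Efgartigimod PH20 SC treatment will be started on day X, which can be the same day as the day the relapse is confirmed". Relapse makes initiation mandatory for off-drug participants. Section 6.3.2 (situation 3A) also lets the investigator start treatment without a relapse.

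**The concern.** A relapse that prompts a dose comes before that dose. The switch-day rule nevertheless files it after the dose whenever the two share a date and the record has no time. Two other parts of the SAP point the opposite way. Footnote b of SAP Table 2 describes a new treatment period as something that follows a relapse. For PD, SAP 2.2.2 treats untimed day 1 samples planned before dosing as predose.

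The relapse proportion, time to relapse and relapse severity are named secondary endpoints for durability of response. For time to relapse the error has one direction: an event replaced by censoring at study end always lengthens the recorded time. Efficacy datasets are reviewed but not independently programmed (SAP 1.8 reserves that for ADSL, ADAE and ADLB), so two readings of the rule might not come to light.

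**Working it through.** The plan states no figure to reproduce here, so the check traces the rules for one participant.

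**Inputs**
- Status CR from study day 1, in the observation phase (assumed).
- First dose on Day X = 57, 113 or 169 (assumed).
- Study end: about 56 weeks (SAP 1.2), so 56 × 7 + 1 = study day 393.
- Time to relapse = end date − start date + 1 (SAP 4.1.2 item 9).

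**Trace for a date-only relapse starting on Day X = 113**
1. SAP 2.2.1 moves the record to treatment period 1.
2. Item 8 closes the observation-phase window when treatment period 1 starts, so no relapse is found there.
3. In treatment period 1 the participant enters in relapse, with no earlier CDA, CR or PR in that period. Items 8 and 9 then do not count it.
4. The observation phase is the first evaluation, so it enters the time-to-relapse table: 393 − 1 + 1 = 393 days, censored.
5. Kept in the observation phase, the same relapse gives 113 − 1 + 1 = 113 days, an event.

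**Observation-phase result by recorded start (days)**

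| Day X | Start 7 days before | Start 1 day before | Start on Day X, timed predose | Start on Day X, date only, SAP as written | Start on Day X, date only, after the fix |
|---|---|---|---|---|---|
| 57 | event 50 | event 56 | event 57 | censored 393 | event 57 |
| 113 | event 106 | event 112 | event 113 | censored 393 | event 113 |
| 169 | event 162 | event 168 | event 169 | censored 393 | event 169 |

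Only the date-only record starting on Day X goes wrong. The same logic applies to a restart after the Off IMP part of treatment period 1.

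**Variant.** If the earlier CR episode is also dated to Day X, the relapse could count in the new period at 113 − 113 + 1 = 1 day. It would then reach the proportion table, but the time-to-relapse table would still show the first evaluation, censored at 393.

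**Relapse proportion (Table 14.2.1.7).** By analogy with the CRoff table, this counts participants with at least one relapse during the study, over all who are evaluable at least once. With E evaluable participants, of whom k lose their only counted relapse, the percentage falls by 100 × k / E points. The documents give neither E nor k. For k = 1 the fall is 100/20 = 5 points if E = 20 and 100/40 = 2.5 points if E = 40 (both assumed).

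**Severity (item 10).** This takes the first BPDAI total score in the relapse interval minus the score at the preceding visit. It does not use phase allocation. It is lost only because the relapse itself is not counted.

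**Duration of sustained remission (item 7).** This also ends at the start of the next treatment period, so the end date is Day X either way.

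**The case against.** The best defence is that items 8 and 9 can be read by date alone. The observation phase ends one minute before the first dose, which is normally still Day X, and SAP 3.1 computes phase duration from that end date. Item 9 sets no phase limit on the relapse date and goes to study end only when there is no relapse. A programmer comparing dates could therefore record an event on Day X. This shows that the SAP is ambiguous. It does not displace the explicit switch-day rule, and the SAP does not say which reading governs.

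Second, the event date is the start of the episode, not its confirmation. The protocol's relapse definition involves lesions accruing over a month, lesions not healing within a week, or daily pruritus, so onset can precede the confirming visit. The SAP does not say whether the recorded start is onset or visit date. This stands: a reader might infer that every relapse confirmed on Day X is lost, but those with an earlier recorded start are counted correctly, and the protocol says only that the two days can coincide.

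Third, a reader might infer that the tables will show a falsely low off-drug relapse rate, or blame efgartigimod for relapses that preceded it. No planned relapse table separates on-drug from off-drug time; results are for the total group, and treatment period 1 itself combines On and Off IMP. If the relapse is counted in the new period, the participant still appears in Table 14.2.1.7. This stands too.

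Finally, Listings 16.2.6.1 and 16.2.6.2 would let a reader trace individual cases. That helps detection but does not correct the tables.

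**Conclusion.** The point holds in limited form and is moderate, not a must-fix. It rests on three conditions: disease-status records have no time part, the recorded relapse start equals the date of first or renewed IMP, and the switch-day rule is applied as written. Then the relapse that prompted dosing can go uncounted, the participant's first time-to-relapse evaluation is censored at study end, and the participant drops out of the relapse proportion and severity tables unless another relapse is counted.

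Relapses with an earlier recorded start, timed predose records and duration of sustained remission are not affected. The number of participants concerned cannot be derived from the documents. It is confined to those with off-drug time, mainly those who rolled over before amendment 2. The study has a safety primary objective and no hypothesis testing, so no formal conclusion depends on this.

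**What to change.** In SAP 2.2.1 and in items 8 and 9 of 4.1.2, state that a date-only relapse starting on the date of first or renewed IMP belongs to the preceding observation phase or treatment period, that the relapse window of that phase or period runs through that date inclusive, and that the relapse is not counted again in the new period. State also whether the recorded episode start means onset or confirmation. Severity under item 10 then follows without reallocating any BPDAI score. Leave the current rule in place for the day 1 evaluability checks of items 1 to 3.

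The cost is a few SAP sentences and a small programming change, with no new data. Time to relapse may look slightly less favourable.
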